Percentages will be calculated as "frequencies" divided by the number of subjects in the population the analysis is based on (i.e. this may include missing data in the denominator).

Form Valid From: 08/03/2024

Form Version:

Record Title: Clinical Statistical Analysis Plan CT-P1-001

Record Title:

Descriptive statistics

Basic descriptive statistics for continuous data comprise:

- Number of observations (N)
- Arithmetic mean
- Standard deviation (SD)
- Minimum (Min)
- Lower quartile (Q1)
- Median
- Upper quartile (Q3)
- Maximum (Max)

Descriptive statistics for continuous variables assumed as log-normally distributed (e. g. PK parameters):

- Number of observations (N)
- Number of observations ≥ LLOQ (NLOQ)
- Arithmetic mean
- Arithmetic SD
- Arithmetic coefficient of variation (CV)
- Geometric mean
- Geometric SD
- Geometric CV (%) (gCV)
- Q1
- Median
- Q3
- Min
- Max

Analysis sets and data review criteria

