measurements, no data transformation of these measurements is required prior to statistical analysis. Minimum and maximum values for vital signs assessed within one day will be analyzed using descriptive summary statistics (including changes from baseline) by treatment group and time point (Day 1, Day 2, Day 3 etc.).

Data distribution for all vital signs (both averages of high-frequency data and single measurements) will be evaluated using the Kolmogorov-Smirnov test and, if applicable, normal/non-normal distribution will be reported. All variables will be expressed both as mean ± standard deviation (SD), as well as medians and interquartile ranges (IQR) in tables and graphical representations of the data. In case a value of one of these parameters is an outlier in a subject, this will be described separately.

Safety laboratory parameters & inflammatory parameters

All safety laboratory parameters (see the study protocol for a full overview) are measured at set intervals during the experimental protocol, as well as during each of the study's follow-up visits. All safety laboratory measurements represent single timepoint measurements, meaning no data transformation prior to analysis needs to be performed. Complete listings for laboratory values will be generated. Laboratory values outside the normal range will be marked. Minimum and maximum values will be reported (including changes from baseline) by treatment group and time point (Day 1, Day 2, Day 3 etc.). In case a value of one of these parameters is an outlier in a subject, this will be described separately.

Data distribution for all safety laboratory parameters will be evaluated using the Kolmogorov-Smirnov test and normal/non-normal distribution will be reported. All variables will be expressed both as mean ± standard deviation (SD), as well as medians and interquartile ranges (IQR) in tables and graphical representations of the data. In case a value of one of these parameters is an outlier in a subject, this will be described separately.

Results from laboratory tests will be summarized by treatment group and time point using descriptive summary statistics, including changes from baseline. Relative changes (for laboratory values) from baseline to follow-up visits (post-study drug administration minus baseline) will be categorized as:

Maximum increase from baseline: (maximum value post-study drug administration – baseline) / baseline

 \geq 1.5, \geq 2.0

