 Maximum decrease from baseline: (baseline - minimum value post-study drug administration) / baseline

≤ 0.5

Form Valid From: 08/03/2024

Form Version:

Record Title: Clinical Statistical Analysis Plan CT-P1-001

Record Title:

A frequency table by treatment dose will be generated for these categorized changes.

In addition, changes from "from within normal range to above normal range" will be evaluated and categorized as:

"changes to at least 1.5-time upper limit normal", "changes to at least twice upper limit normal".

A frequency table by treatment will be generated for these categorized changes from normal at baseline.

In case a value of one of these parameters is an outlier in a subject, this will be described separately.

12-lead ECG parameters

Non-quantifiable differences in ECG's deemed to be of clinical relevance by a clinical investigator will be registered as an (S)AE. For differences in ECG-related (S)AEs, the same ground-rules apply as those listed under reported number of adverse events and local tolerability (please refer to this section). Frequencies of overall interpretation (normal, abnormal and clinically not significant, abnormal and clinically significant) will be tabulated by treatment group and time point.

For numerically quantifiable differences in ECG-parameters (e.g. QTc-time, see the study protocol for a full overview), data distribution will be assessed using the Kolmogorov-Smirnov test and normal/non-normal distribution will be reported. Individual measurement timepoints will be expressed as both mean ± standard deviation (SD), as well as medians and interquartile ranges (IQR).

Extent of exposure

Total exposure [mg] and relative exposure [mg/kg] will be analyzed by descriptive summary statistics.

8.6 **Analysis of secondary endpoints**

Pharmacokinetic data analyses

The PK parameters will be analyzed by descriptive summary statistics. AK1967 concentration-time profiles for individual subjects will be analyzed with non-compartmental approaches using a validated commercially available software package (WinNonlin, version 8.4, Pharsight Corporation, Mountain View, CA). Nominal times will be used in the analysis. For data reported as BLQ and ALQ (below and above limit of quantification, respectively), the low and high limit of detection value will be used in the analysis.

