	14.2.1.2 Safety laboratory & Inflammatory parameters	
Table	Descriptive summary statistics for laboratory parameters at each time point	
Table	Change from baseline in laboratory parameters at each time point per dosing group	
Listing	Listing of individual subject laboratory parameters at each time point	
Table	Descriptive summary statistics for inflammatory parameters	
Listing	Listing of inflammatory parameters	

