	14.2.1.5 Adverse events	
Table	Table of the number and percentage of subjects experiencing adverse events, categorized by severity, potential relationship to the investigational medicinal product (IMP) and dosing group	
Table	Summary table of adverse events by system organ class and preferred term (including changes in vital signs and any laboratory changes)	
Table	Table summarizing local tolerability at the site of i.v. infusion, including any reported reactions or issues	
Listing	Listing of all adverse events by subject, including severity, potential relationship to IMP, and outcome	
Figure	Bar charts or pie charts showing the distribution of adverse events by severity and potential relationship to IMP	

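### The laboratory decrease category in SAP 8.5 is inverted: its cut-off counts subjects with no fall or a fall of up to half, and leaves out every fall of more than half

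*SAP*

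**What the plan says.** Under safety laboratory parameters, SAP 8.5 defines two relative changes from baseline and attaches cut-offs to each.

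- Upward: "Maximum increase from baseline: (maximum value post-study drug administration – baseline) / baseline", with categories ≥ 1.5 and ≥ 2.0.
- Downward: "Maximum decrease from baseline: (baseline - minimum value post-study drug administration) / baseline", with the single category ≤ 0.5.

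The SAP then states: "A frequency table by treatment dose will be generated for these categorized changes". A second categorised table follows. It covers only changes "from within normal range to above normal range", graded as "changes to at least 1.5-time upper limit normal" and at least twice that limit. Safety laboratory parameters are among the primary endpoints (SAP 5.1).

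SAP 6.3 separately defines relative change with the opposite sign, post-dose minus baseline over baseline, and says percentages are "divided by the number of subjects in the population the analysis is based on", which can include subjects with missing data.

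**The concern.** The downward measure is positive for a fall and approaches 1 as the value approaches zero. A category meant to pick out marked falls therefore needs a lower bound. The SAP gives an upper bound, so the category selects the unremarkable subjects and drops the ones the table exists to find.

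This is the only rule in the SAP that counts subjects by the size of a downward laboratory change. The normal-range table looks upward only. The adverse event output, "Summary table of adverse events by system organ class and preferred term (including changes in vital signs and any laboratory changes"), appears to count a laboratory change only when it has been reported as an event. Haemoglobin, leukocytes, thrombocytes and fibrinogen are all on the safety list, and for these a fall matters. Because the table is laid out by dose, an inverted category also inverts any dose trend in it.

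**Working it through.** The SAP gives no computed figure here, so there is nothing to reproduce. The check is to evaluate the rule as written and compare it with the consistent alternatives.

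**Inputs.** Formula and cut-offs from SAP 8.5; dose groups of 6 from SAP section 3, Table 2; denominator rule from SAP 6.3. No event rate or distribution is assumed.

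**Step 1: which subjects are selected.** Let D = (baseline − minimum)/baseline, with an illustrative baseline of 100.

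| Minimum | D | As written: D ≤ 0.5 | D ≥ 0.5 | Minimum/baseline ≤ 0.5 |
|---|---|---|---|---|
| 120 | −0.20 | counted | no | no |
| 100 | 0.00 | counted | no | no |
| 75 | 0.25 | counted | no | no |
| 51 | 0.49 | counted | no | no |
| 50 | 0.50 | counted | counted | counted |
| 49 | 0.51 | no | counted | counted |
| 25 | 0.75 | no | counted | counted |
| 10 | 0.90 | no | counted | counted |

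The last two columns agree in every row, because D = 1 − minimum/baseline. The written rule agrees with them only at a fall of exactly 50%.

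**Step 2: whether the sign convention in SAP 6.3 rescues it.** On that scale a fall is negative. (Minimum − baseline)/baseline ≤ 0.5 would count every fall of any size and every minimum up to 1.5 times baseline, so it does not.

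**Step 3: size in one dose group.** For a given laboratory parameter, let k be the number of the 6 subjects with a fall of more than half and e the number at exactly half, with complete data.

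- Written count = 6 − k
- Corrected count = k + e
- Difference = 6 − 2k − e

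| k | e | Corrected | As written |
|---|---|---|---|
| 0 | 0 | 0/6 (0%) | 6/6 (100%) |
| 1 | 0 | 1/6 (16.7%) | 5/6 (83.3%) |
| 2 | 0 | 2/6 (33.3%) | 4/6 (66.7%) |
| 3 | 0 | 3/6 (50%) | 3/6 (50%), opposite subjects |
| 1 | 1 | 2/6 (33.3%) | 5/6 (83.3%) |

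Each additional subject with a fall of more than half moves the written percentage by −1/6, or −16.7 percentage points.

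**Step 4: the increase rule.** (Maximum − baseline)/baseline ≥ 1.5 means maximum ≥ 2.5 × baseline, and ≥ 2.0 means maximum ≥ 3.0 × baseline. The direction is right, so this rule is coherent. If multiples of baseline were intended, a maximum from 1.5 to below 2.5 times baseline is missed by the first cut-off, and one from 2.0 to below 3.0 times by the second.

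**The case against.** The strongest reply is that this is an editorial slip with little consequence. Much of that stands. The table is descriptive, and SAP 3.1 plans no comparative analysis of the primary endpoint. The protocol's account of the safety board's review (10.3 and 12.10) does not mention the table. Listings, out-of-range marking, reported minima, separate description of outliers and "Change from baseline in laboratory parameters at each time point per dosing group" would all still reveal large falls. A table showing 100% with a marked decrease when nobody had one would probably also be noticed. These points limit the severity; they do not make the rule right.

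A second reply is that the true count can be recovered by subtraction, or that SAP 6.2, which asks for all possible categories to be shown, would bring in the complement. Subtraction works only with complete data. SAP 8.2 does not impute missing values and SAP 6.3 may keep missing subjects in the denominator, so 5/6 could mean one large fall or one subject without data. The SAP names no complementary category.

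A third reply is that a minus sign was lost. With the formula as printed, ≤ −0.5 would select minima of at least 1.5 times baseline, so a minus alone does not repair it; the formula would also have to take the sign used in SAP 6.3. That remains a possible origin, and under it the increase cut-offs would be ordinary relative changes with nothing to correct. The increase scale is therefore a query, not an error.

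Finally, the point depends on one printed sign, which should be checked against the source page. The neighbouring increase cut-offs read as ≥, and the signs are kept apart elsewhere (SAP 6.3; Protocol 6.3), so a misread is unlikely but not excluded.

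**Conclusion.** The concern holds. As written, the decrease category does the opposite of what its label says: it excludes every fall of more than half and includes subjects with no fall. Within a dose group of 6, the tabulated count is 6 − k where it should be k + e, for each laboratory parameter, assuming complete data. The error is largest when no one has a large fall (6/6 instead of 0/6), and it turns a rising dose trend into a falling one.

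This should be fixed, though it threatens no main conclusion, since it affects one descriptive table on a primary safety endpoint. Confidence is high that the rule is wrong as it reads, subject to the check of the printed sign. Confidence is low on the cause: a reversed inequality, a cut-off meant for minimum/baseline, or a sign lost from a signed change. All three lead to the same corrected decrease rule. Only the second would also imply that the increase cut-offs are on the wrong scale; the set 1.5, 2.0 and 0.5, and the use of 1.5 and twice as multiples of the upper limit of normal, lean that way without proving it.

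**What to change.** 1. In SAP 8.5, write the decrease category as minimum/baseline ≤ 0.5, or equivalently (baseline − minimum)/baseline ≥ 0.5.
2. In the same edit, state the scale of the increase cut-offs. If multiples of baseline were intended, write maximum/baseline ≥ 1.5 and ≥ 2.0. If relative increases were intended, keep the formula and say that they correspond to 2.5 and 3.0 times baseline.
3. Add the by-dose frequency table to the output list in SAP section 9 (14.2.1.2), which does not name it. The list also omits the normal-range shift table, which could be added at the same time.

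The cost is one or two lines of SAP text, an entry or two in the output list and the matching table code. Data collection does not change. Items 2 and 3 are tidying; item 1 is the correction that matters.

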6.2 Inclusion criteria

In order to be eligible to participate in this study, a subject must meet all of the following criteria:

- 1. Written informed consent to participate in this trial prior to any study-mandated procedure.
- 2. Male subjects aged 18 to 35 years inclusive.
- 3. Subjects have to agree to use a reliable way of contraception with their partners from study entry until one month after study drug administration.
- 4. BMI between 18 and 30 kg/m², with a lower limit of body weight of 50 kg and an upper limit of 100 kg.
- 5. Healthy as determined by medical history, physical examination, vital signs, 12-lead electrocardiogram, and clinical laboratory parameters.

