6.3 Exclusion criteria

A potential subject who meets any of the following criteria will be excluded from participation:

- 1. Unwillingness to abstain from any medication, including recreational drugs or vitamin supplements during the course of the study and within two days prior to the treatment day.
- 2. Unwillingness to abstain from alcohol within one day prior to the treatment day until one day after the treatment day.
- 3. Surgery or trauma with significant blood loss or blood donation within one month prior to the treatment day.
- 4. History, signs or symptoms of cardiovascular disease, in particular:
 - a. History of frequent vasovagal collapse or of orthostatic hypotension
 - b. Resting pulse rate ≤45 or ≥100 beats/min
 - c. Hypertension (RR systolic >160 or RR diastolic >90 mmHg)
 - d. Hypotension (RR systolic <100 or RR diastolic <50 mmHg)
 - e. Conduction abnormalities on the ECG consisting of a 1st degree atrioventricular block or a complex bundle branch block
 - f. Any chronic cardiac arrhythmias (except PAC's, PVC's)

EU CT: 2023-507035-37-00

- Renal impairment: plasma creatinine >120 μmol/L
- 6. Liver function tests (alkaline phosphatase, AST, ALT and/or y-GT) above 2x the upper limit of normal.
- 7. History of asthma
- 8. Atopic constitution
- 9. CRP above 2x the upper limit of normal, or clinically significant acute illness, including infections, within two weeks prior to the treatment day.
- 10. Treatment with investigational drugs or participation in any other clinical trial within 30 days prior to the treatment day.
- 11. Known or suspected of not being able to comply with the trial protocol.
- 12. Known hypersensitivity or allergic reactions to drug compounds, (i.e. previous adverse drug reactions).
- 13. Inability to personally provide written informed consent (e.g. for linguistic or mental reasons) and/or take part in the study.

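### The laboratory shift table counts only upward moves from a normal baseline, and the relative-change table beside it, with ambiguous cut-offs and a reversed fall rule, only partly fills the gap

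*SAP*

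**What the plan says.** SAP 8.5 plans two frequency tables for safety laboratory values.

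- **ULN table.** It covers changes "from within normal range to above normal range", in two categories: at least 1.5 x ULN and at least 2 x ULN. The population is fixed by the next sentence: "A frequency table by treatment will be generated for these categorized changes from normal at baseline". There is no category for the lower limit of normal (LLN).
- **Relative-change table.** It is by dose, with no condition on baseline. Maximum increase is (maximum − baseline)/baseline, with categories ≥ 1.5 and ≥ 2.0. Maximum decrease is (baseline − minimum)/baseline, with the single category ≤ 0.5.

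Protocol 6.3 excludes men with "Liver function tests (alkaline phosphatase, AST, ALT and/or y-GT) above 2x the upper limit of normal" and men with "CRP above 2x the upper limit of normal". Values above 1 and up to 2 x ULN are therefore not excluded by these criteria.

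SAP 8.2 sets the laboratory baseline as the sample before dosing, not the screening sample. SAP 8.5 also provides complete listings with out-of-range values marked, minima and maxima with change from baseline by group and day, and a separate description of outliers. Section 9 lists an adverse event table that takes in laboratory changes. Neither frequency table appears in the section 9 laboratory output list.

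**The concern.** Safety laboratory parameters are part of the primary endpoint, and these two tables are what turn them into counts of men by dose. A man whose ALT is above normal before dosing can never enter the ULN table for ALT, however high it goes. A man whose haemoglobin, leukocytes, thrombocytes, sodium or fibrinogen drops out of the normal range has no cell in that table either. Whether such men are counted at all then depends on the relative-change table, whose cut-offs are unclear and which makes no reference to the normal range. With 6 men per dose, one man is 1/6 = 17% of a dose group, so a single unidentified case would matter to the tabulated picture.

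**Working it through.** The plan states no figure to reproduce. The check applies the two printed rules to example courses.

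**Inputs.** ULN table: baseline ≤ 1 x ULN and post-dose maximum ≥ 1.5 or ≥ 2 x ULN (SAP 8.5). Relative-change formulas and cut-offs: SAP 8.5. Entry limit of 2 x ULN: Protocol 6.3. The example courses are mine. The documents give no lower limits of normal, so 135 for sodium is an assumption.

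**Two readings of the increase cut-offs** (b = baseline, m = maximum):

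- As printed, (m − b)/b ≥ 1.5 or ≥ 2.0, so m must reach 2.5b or 3b. From 2.0 x ULN that is 5.0 or 6.0 x ULN. SAP 6.3 defines relative change by the same form of formula, which favours this reading.
- As ratios, m/b ≥ 1.5 or ≥ 2.0, so m must reach 1.5b or 2b. From 2.0 x ULN that is 3.0 or 4.0 x ULN. The values 1.5, 2.0 and 0.5 look like ratios to baseline, which favours this one.

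**Rises (in multiples of ULN):**

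| Baseline → maximum | ULN table | Increase as printed | Ratio |
|---|---|---|---|
| 0.9 → 1.8 | counted (≥ 1.5) | 0.9/0.9 = 1.00, no | 2.00, yes |
| 1.4 → 2.05 | not eligible | 0.65/1.4 = 0.46, no | 1.46, no |
| 1.9 → 2.8 | not eligible | 0.9/1.9 = 0.47, no | 1.47, no |
| 1.9 → 4.7 | not eligible | 2.8/1.9 = 1.47, no | 2.47, yes |
| 1.8 → 4.5 | not eligible | 2.7/1.8 = 1.50, yes | 2.50, yes |
| 2.0 → 6.0 | not eligible | 4.0/2.0 = 2.00, yes | 3.00, yes |

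Rows two and three end above 2 x ULN and are in no count on either reading. Row four is missed only on the printed formula.

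**Falls** (n = minimum):

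| Course | As printed, (b − n)/b ≤ 0.5 | Ratio, n/b ≤ 0.5 |
|---|---|---|
| No change | 0, in | 1.00, out |
| Sodium 140 → 125 | 15/140 = 0.107, in | 0.893, out |
| Fall of 51% | 0.51, out | 0.49, in |
| Fall of 70% | 0.70, out | 0.30, in |

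As printed, the category holds men with no fall and drops those with the largest falls, so being in it identifies nothing. Read as a ratio, it counts falls of half or more and misses the sodium case. Neither reading uses the LLN.

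**The case against.** The strongest reply is that a reader might infer that every large rise from a raised baseline goes uncounted. The documents do not support that. The relative-change table has no baseline condition and counts 1.8 → 4.5 or 2.0 → 6.0 x ULN on either reading.

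A reader might also infer that the dose summaries would show nothing for an affected man. That is not so: an extreme value would show in the group minimum or maximum, be marked in the listing and possibly be described as an outlier. With 6 men per group, individual values are easy to see. Under Protocol 10.3 and 12.10 the dose-escalation decision rests on the safety board's review of laboratory data and is not stated to depend on these tables.

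Nor should examples mix readings. Thrombocytes falling from 200 to 105 give 95/200 = 0.475, which meets the printed decrease rule. That case escapes only on the ratio reading (0.525), and on that reading the 1.9 → 4.7 rise is counted.

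Finally, the affected men may be few. Protocol 6.2 requires subjects to be "Healthy as determined by medical history, physical examination, vital signs, 12-lead electrocardiogram, and clinical laboratory parameters", and the entry limits do not fix the pre-dose value.

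All of this stands and limits the size of the point. It does not close the gap: listings and extremes do not count men by dose and baseline status, the SAP does not define an outlier, and no laboratory threshold for an adverse event is given.

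**Conclusion.** The point holds in a limited form. The ULN table leaves out raised baselines and all low-side shifts, and the relative-change table fills the gap only in part.

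- **Rises.** From a baseline of 2.0 x ULN, what escapes both tables runs to just under 3.0 x ULN on the ratio reading and just under 5.0 x ULN on the printed formula.
- **Falls.** No count is tied to the lower limit of normal. A shift below normal that is a fall of less than half is not identified on either reading.
- **Drafting.** The increase cut-offs are ambiguous, and the decrease inequality as printed runs the wrong way for a rule meant to flag large falls.

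The data are not lost. What is incomplete is the count by dose for part of the primary safety endpoint. The size in practice depends on how many men have a raised pre-dose value, which the documents do not give. The 17% figure applies only if a dose group contains such a man. The sodium example rests on the assumed lower limit of 135.

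**What to change.** 1. Replace the ULN table with a shift table by dose for all subjects. Cross the baseline category (below, within or above the normal range) with the worst post-dose category in each direction: below LLN on the low side; above ULN, ≥ 1.5 x ULN and ≥ 2 x ULN on the high side.
2. For baselines above ULN, also count ≥ 1.5 and ≥ 2 times the man's own baseline. Without this, a man entering above 1.5 x ULN would fall in that category with no change at all.
3. State whether the relative-change cut-offs of 1.5 and 2.0 are increases or ratios to baseline.
4. Correct the decrease rule so that it counts a fall of at least half.
5. Add both frequency tables to the section 9 output list.

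The shift table places 1.9 → 2.8 x ULN in the raised-baseline, ≥ 2 x ULN cell, and sodium 140 → 125 in the normal-to-low cell. The cost is SAP wording and a few more table rows from data already collected, plus some background counts, including from placebo.

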10.2 Randomisation, blinding and treatment allocation

The randomization procedure is stratified into the three groups, consisting of 8 subjects each, with sequential groups being administered increasing doses of Procizumab (table 7). Six subjects of each group will be treated with active medication and two subjects with placebo. These groups are further divided into two randomization blocks consisting of four subjects each (one placebo treatment and three active medication treatment). This is done as an additional safety measure, to ensure an even spread of placebo-treated subjects over all groups (using this approach, the study can never start with two placebo-treated subjects).

Group 1		Gro	up 2	Group 3				
Randomization	Randomization	Randomization	Randomization	Randomization	Randomization			
block 1 (R1.1	block 2 (R.2.1	block 3 (R3.1	block 4 (R4.1	block 5 (R5.1	block 6 (R6.1			
to R.1.4)	R.2.4)	to R.3.4)	to R.4.4)	to R.5.4)	to R.6.4)			
1x placebo	1x placebo	1x placebo	1x placebo	1x placebo	1x placebo			
3x 3.0 mg/kg	3x 3.0 mg/kg	3x 6.0 mg/kg	3x 6.0 mg/kg	3x 12.0 mg/kg	3x 12.0 mg/kg			
AK1967	AK1967	AK1967	AK1967	AK1967	AK1967			

Table 7. Block-randomization groups of different study groups

A randomization list will be created by unblinded research staff prior to the treatment day. This list contains the randomization numbers, consisting of a two-digit number preceded by capital 'R' to identify this number as being the randomization number. The first digit corresponds with the randomization block (1 to 6). The second digit corresponds with the randomization number within the randomization block, starting with 1 (for example R.1.1 for randomization block 1, subject 1, followed by R.1.2, R.1.3, onwards to R.6.4). The unblinded research staff will assign a treatment group (active medication or placebo) at random to each number on the list. They will start with randomizing block 1 and will continue until they reach randomization block 6.

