5.1 Endpoints for the primary objectives

Safety analysis:

The endpoints for the primary objective are to determine over the 28 days study period:

- Reported number of adverse events from baseline (just prior to the start of IMP administration) up until the last follow-up visit 28 days after IMP administration.
- (Changes in) vital signs from baseline to during the first 24 hours after start of IMP administration, as well as during the six follow-up visits. Vital signs included are: heart rate, blood pressure, peripheral oxygen saturation and body temperature.
- Local tolerability at site of i.v. infusion of the IMP.
- Safety laboratory parameters from baseline (just prior to the start of IMP administration) up until the last follow-up visit 28 days after IMP administration. Laboratory parameters included are: Hb, Htc, leukocytes, leukocyte differential blood count, thrombocytes, sodium, potassium, creatinine, urea, alkaline phosphatase, ALT, AST, bilirubin, GGT, CK, CRP, PT, APTT, fibrinogen.
- 12-lead electrocardiogram (ECG) at baseline (screening), compared to ECG's performed 2 hours, 9 hours and 7 days after start of IMP administration.

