	14.2.1.3 ECG	

Filing: https://fourteenfour.dhcvisioncloud.com/dhcvision/document.jsp?key=DATABASE:1001;IO:1527897 Page 19 of 22

Form Valid From: 08/03/2024

Form Version: 1

Record Title: Record Title: Clinical Statistical Analysis Plan CT-P1-001

Table	Summary tables of ECG parameters	
	Change from baseline in ECG parameters at each time points per dosing group	
Listing	Listing of individual subject ECG results at each time point	
Figure	Line graphs showing the mean and standard deviation of ECG parameters over time	

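### The planned summary of ECG interpretations gives counts per group and time point only, so it cannot show how many men moved from normal at screening to abnormal after dosing

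*SAP*

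**What the plan says.** SAP 5.1 lists the ECG among the primary safety endpoints: "12-lead electrocardiogram (ECG) at baseline (screening), compared to ECG's performed 2 hours, 9 hours and 7 days after start of IMP administration". SAP 8.2 confirms screening as the ECG baseline.

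SAP 8.5 then treats the ECG in three ways:

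- **Overall interpretation, three categories.** "Frequencies of overall interpretation (normal, abnormal and clinically not significant, abnormal and clinically significant) will be tabulated by treatment group and time point".
- **Clinically relevant changes that cannot be measured.** "Non-quantifiable differences in ECG's deemed to be of clinical relevance by a clinical investigator will be registered as an (S)AE".
- **Numeric parameters such as QTc.** Mean with SD and median with IQR at each time point.

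The output list in SAP section 9, under 14.2.1.3, adds a table, "Change from baseline in ECG parameters at each time points per dosing group", and a listing, "Listing of individual subject ECG results at each time point". No shift table for the interpretation category appears there, in 8.5 or in 8.7.

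For laboratory values, by contrast, SAP 8.5 does count moves out of the normal range: "A frequency table by treatment will be generated for these categorized changes from normal at baseline".

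**The concern.** A frequency table gives the margins of the screening-by-post-dose cross-classification and leaves out its cells. A man who becomes abnormal and a man whose tracing returns to normal cancel in the count, so a level or falling count does not show that nobody changed. The change-from-baseline table does not help here, because SAP 6.3 defines change as the post-dose value less the baseline value, and a category has no such difference.

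At stake is the visibility of minor new findings in a first-in-human trial. A change judged not clinically significant in one man is unremarkable. The same change arising in several men as the dose rises from 3 to 6 to 12 mg/kg would be worth seeing in a summary.

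**Working it through.** The plan states no figure on this point, so there is none to reproduce. The check has three parts.

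**1. What the margins determine.** Protocol 10.2 gives the group size: "Six subjects of each group will be treated with active medication and two subjects with placebo". Three dose groups give 3 × 2 = 6 placebo men, so each of the four analysis groups has n = 6. Let b be the number abnormal at screening and t the number abnormal at one post-dose time. The number of new abnormalities k then satisfies

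max(0, t − b) ≤ k ≤ min(t, 6 − b).

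| b | t | k can be |
|---|---|---|
| 0 | 1 | 1 only |
| 1 | 1 | 0 to 1 |
| 2 | 2 | 0 to 2 |
| 3 | 3 | 0 to 3 |

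This needs no assumed rate. With b = 0 the table is unambiguous at any single time point. Across time points it is not: 1 of 6 abnormal at 2 h, at 9 h and on day 7 could be one man or three.

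**2. Whether b can exceed 0.** Inclusion 5 requires health as judged partly by the 12-lead ECG. The synopsis requires no clinically relevant screening findings. Exclusion 4 covers cardiovascular history, signs or symptoms and gives particular examples, among them "Conduction abnormalities on the ECG consisting of a 1st degree atrioventricular block or a complex bundle branch block", chronic arrhythmia (PACs and PVCs excepted) and pulse limits. These rules narrow the pool but do not bar a tracing read as abnormal and not clinically significant. Under Protocol 10.1 screening may precede dosing by up to 28 days, so a transient finding may be gone by the next ECG.

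**3. How often the count would fail to rise.** The documents give no rates, so all three are assumptions: p, abnormal at screening; q = 15% or 30%, a normal man becoming abnormal; s = 25% or 50%, an abnormal man reading normal later. For one post-dose time and two categories,

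b ~ Bin(6, p), k ~ Bin(6 − b, q), r ~ Bin(b, s),

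where r is the number who resolve. The quantity is P(r ≥ k and k ≥ 1) / P(k ≥ 1), with P(k ≥ 1) = 1 − (1 − (1 − p)q)^6.

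Example with p = 10%, q = 15%, s = 50%: P(k ≥ 1) = 1 − (1 − 0.135)^6 = 0.581. Summing the joint probabilities over b, k and r gives P(r ≥ k and k ≥ 1) = 0.104. The ratio is 0.104 / 0.581 = 0.18.

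| p | q 15%, s 25% | q 15%, s 50% | q 30%, s 25% | q 30%, s 50% |
|---|---|---|---|---|
| 0% | 0% | 0% | 0% | 0% |
| 5% | 5% | 9% | 3% | 6% |
| 10% | 9% | 18% | 7% | 13% |
| 20% | 18% | 34% | 14% | 26% |
| 30% | 27% | 48% | 22% | 39% |
| 40% | 36% | 60% | 30% | 51% |

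The range is 3-18% for p of 5-10%, and 14-60% for p of 20-40%.

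**The case against.** The case for leaving the plan alone has substance.

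- **Other outputs cover much of the ground.** A QTc change would appear in the change-from-baseline table, although the documents name QTc only as an example, so coverage of PR and QRS is unconfirmed. Clinically relevant changes reach the AE tables. The listing covers 24 men with four scheduled ECGs each, 24 × 4 = 96 readings, which can be traced by hand.
- **Escalation does not wait on this table.** Protocol 10.3 has the DSMB receive a report with ECGs per dose group before each escalation. The format of that display is not given.
- **The larger percentages need high screening rates.** In screened men aged 18 to 35, a rate of 20-40% is unsupported by any document. The calculation also uses a single time point. The planned table shows three separately, so hiding a persistent change would take offsetting at each of them.

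All of this stands and limits the point. What it leaves is a non-quantifiable change judged not significant, which no planned summary shows as new. The listing preserves the data but leaves the comparison to unplanned reading.

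A reader might go further and infer that the plan contradicts its own endpoint, taking that to be each man's ECG against his own baseline. The documents do not say that. The protocol synopsis and SAP section 2 define the safety endpoints as differences between placebo and dosage groups, and a table of counts by time point can set screening beside post-dose if it includes screening. A reader might also infer that only the named conduction and rhythm disorders are barred at entry. Exclusion 4 is worded as a set of examples, and inclusion 5 and the synopsis narrow entry further.

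**Conclusion.** The gap is real and modest. The planned summary of ECG interpretation bounds the number of newly abnormal men without giving it, and the bound is loose whenever some men are abnormal at screening. That follows from the table's form and rests on no assumption.

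How often it would matter cannot be settled from the documents. On the assumed rates the effect is nil with normal screening tracings throughout, small at 5-10% abnormal and material only at 20% or more. No collected information is lost, and no test is biased, since SAP 3.1 plans no comparative analysis of the primary endpoint. A reader might infer that new conduction or repolarisation changes would go unseen; the parameter table, the AE route and the listing do not support that.

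**What to change.** In SAP 8.5, under 12-lead ECG parameters, and in the 14.2.1.3 output list, add a shift table by treatment group. It should set the screening interpretation against the interpretation at 2 h, 9 h and day 7, and against the worst post-dose interpretation. Add the number of men with a new or worsened interpretation; the worst post-dose comparison and this count also settle whether abnormal readings at different times belong to the same man. This follows the approach the SAP already takes for laboratory values. The existing frequency table can stay.

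The cost is one SAP sentence and one table. It needs no new data and no change to conduct or sample size.
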